3.2 Exclusion Criteria

- 3.2.1 Patients who receive an autologous tissue reconstruction.
- 3.2.2 Patients who receive a unilateral reconstruction.
- 3.2.3 Patients who are expected to undergo axillary lymph node dissection
- 3.2.4 Patients who have undergone breast irradiation
- 3.2.5 Patients who abuse narcotics or have chronic pain (using greater than 40 mg equivalents of oxycodone per day)
- 3.2.6 Patients who are wards of the state
- 3.2.7 History of allergic reactions attributed to compounds of similar chemical or biologic composition to bupivacaine or liposomal bupivacaine.
- 3.2.8 Pregnant women are excluded from this study because pregnancy precluded immediate breast reconstruction in our patient population.
- 3.2.9 Patients who weigh less than 50 kg, as there can be dose related toxicities of the bupivacaine dosing used in this study
- 3.2.10 Patients with moderate-severe hepatic or renal impairment because of the increased risk of toxicity.
- 3.2.11 Patients receiving bilateral mastectomy with immediate pre-pectoral implant based breast reconstruction

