5.2.2 Morphine equivalents used within the first month postoperatively

THE USE OF LIPOSOMAL BUPIVACAINE FOR PAIN CONTROL FOLLOWING MASTECTOMY AND IMMEDIATE IMPLANT BASED BREAST RECONSTRUCTION

Wake Forest Baptist Comprehensive Cancer Center
CCCWU # 99517

- 5.2.2.1 The number of doses of oral narcotics (hydrocodone-acetaminophen 1 tablet) for patients with immediate tissue expander reconstruction without other measure of pain control has been 4.2 at 24 hours and 4.0 at 48 hours¹⁷. This is approximately 3.3 morphine equivalents
- 5.2.2.2 We would expect the patients treated with liposomal bupivacaine to use an average of 2.5 intravenous morphine equivalents at the 48-hour point and decreased morphine equivalents in the liposomal bupivacaine over the first postoperative month.
- 5.2.3 Length of stay for hospitalization after mastectomy and breast reconstruction
 - 5.2.3.1 Length of stay for patients undergoing mastectomy and immediate reconstruction has been shown to be 41-47 hours on average²¹
 - 5.2.3.2 We believe liposomal bupivacaine will shorten this time to 36 hours±12 in the liposomal bupivacaine group, but not in the bupivacaine groups.
- 5.2.4 Readmission rates to the hospital within 2 months after mastectomy and breast reconstruction
 - 5.2.4.1 Patients who underwent tissue expander breast reconstruction have a readmission rate of approximately 4.34%²². We anticipate a readmission rate of approximately 2% Patients will be informed that if they are expected to undergo an axillary lymph node dissection at the time of surgery then they will be excluded from the study. Patients who are undergoing sentinel lymph node biopsies will be included in the study, but if their nodes are positive and there is an intraoperative decision to pursue axillary lymph node dissection they will subsequently be excluded from the study.
- 5.2.5 Frequency of postoperative opioid related adverse effects within the first week of surgery. This includes nausea, vomiting, pruritus, allergy, respiratory depression.
 - 5.2.5.1 After immediate breast reconstruction with implants, patients receiving bupivacaine had a 40% incidence of nausea and vomiting. Those not receiving a local anesthetic had a 75% incidence of nausea and vomiting¹⁷
 - 5.2.5.2 We predict a 30% incidence of opioid related adverse events in our liposomal bupivacaine group
- 5.2.6 Trajectory of postoperative recovery from pain within the first 2 months

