10.2 Analysis of Secondary Objective

10.2.1 For the area under the curve of pain scores at 48 hours, prior studies have found that the area under the curve for pain scores at 72 hours for liposomal bupivacaine infiltration is $441 +/- 182$ and for bupivacaine infiltration is $461 +/- 181^{20}$. A sample size of 40 in each group will have 80% power to detect a difference in means of approximately 25% (115 units) between a Bupivacaine mean, m_1 , of 461 and a Liposomal Bupivacaine mean, m_2 , of 346 assuming that the common standard deviation is 181 using a two group t-test with a 0.05 two-sided significance level. Our study will be powered to detect this difference; we will use an independent t-test to assess statistical significance.

10.2.2 For postoperative narcotic use, prior studies have found the average use of morphine equivalents at 48 hours after mastectomy and tissue expander placement is 3.3¹⁷. This study will also have the ability to detect an effect size of 0.6 between groups, with 45 per group, a two-sided alpha of 0.05, and 80% power. We would expect the patients treated with liposomal bupivacaine to be have a lower average use. We will use an independent t-test to test for differences between groups; if the data are not normally distributed, a log transformation will be used prior to using the t-test.

10.2.3 For length of stay, the reported LOS has been shown to be 41-47 hours on average²¹. We believe Exparel will shorten this time; the study will have the ability to detect an effect size of 0.60 between the 2 groups. We will use an independent t-test to test for differences between groups; if the data are not normally distributed, a log transformation will be used prior to using the t-test.

10.2.4 For readmission rates, patients who underwent tissue expander breast reconstruction have a readmission rate of approximately 4.34%²². We anticipate a readmission rate of approximately 2%. Our study is not powered to detect differences in the 2 arms in this parameter.

10.2.5 For opioid related adverse effects, we predict a 50% incidence of opioid related adverse events in our study. With 45 per group, our study is not powered to detect differences between the 2 arms unless the difference is much larger than anticipated. With a 60%

THE USE OF LIPOSOMAL BUPIVACAINE FOR PAIN CONTROL FOLLOWING
MASTECTOMY AND IMMEDIATE IMPLANT BASED BREAST RECONSTRUCTION

Wake Forest Baptist Comprehensive Cancer Center
CCCWU # 99517

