10.3 Power and Sample Size

We will have a power of 80%, as described in 10.1.1, with a sample size of 25 patients in each arm for a total of 50 patients

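### Narcotic use is compared without adjustment for preoperative opioid dose, although patients using up to 40 mg oxycodone equivalents a day may enter; the comparison stays unbiased but loses power at 25 per arm

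*Combined protocol and SAP*

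**What the plan says.** - **Eligibility.** Section 3.2.5 excludes "Patients who abuse narcotics or have chronic pain (using greater than 40 mg equivalents of oxycodone per day". The Appendix A checklist repeats the criterion. Nothing else in section 3 removes a patient who takes a daily opioid at or below 40 mg.
- **Endpoint.** Section 5.2.2 defines it as "Morphine equivalents used within the first month postoperatively". Under section 6.1, narcotics used in hospital are recorded and converted, and a diary covers the time after discharge. Neither source separates a continued habitual dose from new use.
- **Expected effect.** Section 5.2.2.1 cites hydrocodone-acetaminophen doses of 4.2 at 24 hours and 4.0 at 48 hours and adds: "This is approximately 3.3 morphine equivalents". Section 5.2.2.2 expects the liposomal arm to "use an average of 2.5 intravenous morphine equivalents at the 48-hour point". No difference is given for the month.
- **Analysis.** Section 10.2.2 states: "We will use an independent t-test to test for differences between groups". It adds a log transformation if the data are not normal. It names no covariate, stratification or baseline subtraction. Predictive factors appear only in 10.2.6.2, for the pain trajectory.
- **Baseline data.** Section 6.1 lists demographics, history, existing pain and questionnaires, but not opioid dose. Appendix A offers a tick box and a source column. Appendix G asks for drug and pill count over 24 hours, without strength, and section 6.1 ties it to the visits from week 1 onward.

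**The concern.** A patient who took an opioid daily before surgery and continues it will show use that the infiltrated drug did not cause. The expected arm means are small (3.3 and 2.5 units over 48 hours), so a continued daily dose may be large beside them. With 25 patients per arm, a few such patients widen the spread of the outcome and may fall unevenly between the arms. The unadjusted test treats all of that as noise, although the dose that explains part of it has to be established anyway to apply 3.2.5. At stake is the power and readability of the narcotic-use comparison, a secondary endpoint.

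**Working it through.** **1. The plan's own figure.** Section 10.2.2 claims "ability to detect an effect size of 0.6 between groups, with 45 per group, a two-sided alpha of 0.05, and 80% power". The exact two-sample t-test needs 44.6 per group, so 45 reproduces (power 0.804). Section 10.3, however, enrols "with a sample size of 25 patients in each arm for a total of 50 patients". At 25 per arm, power for 0.6 SD is 0.55, and the effect detectable with 80% power is 0.81 SD. There is little power to spare before any opioid user enrols.

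**2. One patient at the ceiling, raw scale.** Assume the full 40 mg a day continues after surgery and is counted.

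- Extra over 48 hours: 40 × 2 = 80 mg oxycodone.
- Spread over the arm: 80 / 25 = 3.2 mg per patient.
- Shift of the arm mean: 80c / 25, where c is morphine-equivalent units per mg oxycodone. The documents do not give c, so every value below is an assumption.
- Expected difference: 3.3 − 2.5 = 0.8. Break-even c: 0.8 × 25 / 80 = 0.25 (0.45 with 45 per arm).

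**3. The same patient, log scale.** The shift in the log mean is ln((m + 80c)/m)/25, for a patient who would otherwise sit at the arm mean m (3.3 or 2.5). The expected effect is ln(3.3/2.5) = 0.278.

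| c (assumed) | Extra units, 48 h | Raw shift, 25 per arm | Raw shift, 45 per arm | Log shift, 25 per arm | Share of 0.278 |
|---|---|---|---|---|---|
| 0.25 | 20 | 0.80 | 0.44 | 0.078–0.088 | 28–32% |
| 1/3 | 26.7 | 1.07 | 0.59 | 0.088–0.098 | 32–35% |
| 0.5 | 40 | 1.60 | 0.89 | 0.103–0.113 | 37–41% |
| 1 | 80 | 3.20 | 1.78 | 0.129–0.140 | 46–50% |
| 1.5 | 120 | 4.80 | 2.67 | 0.145–0.156 | 52–56% |

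**4. The scale implied in 5.2.2.1.** The text equates either about 4 tablets or the two-day total of 8.2 tablets with 3.3 units; it does not say which. Tablet strength (5 to 10 mg) and oxycodone-to-hydrocodone potency (1 to 1.5) are my assumptions.

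- Upper end: 3.3 / (4.0 × 5) = 0.165 units per mg; 80 × 1.5 × 0.165 / 25 = 0.79.
- Lower end: 3.3 / (8.2 × 10) = 0.040 units per mg; 80 × 1 × 0.040 / 25 = 0.13.

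On this scale one patient moves the raw mean by less than 0.8 throughout.

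**5. Effect on power.** Simulation with 25 per arm, lognormal data and SD 0.8 / 0.6 = 1.33 (implied, not stated in the plan).

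- One patient with 40 extra units: raw t-test power falls from 0.57 to 0.01 or less, whichever arm holds the patient. Log-scale power is 0.72 with no such patient, 0.13 with one in the liposomal arm and 0.79 with one in the control arm.
- With 20 extra units in the liposomal arm, log-scale power is 0.26.
- With no treatment effect, the false-positive rate does not rise above 5%.

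**6. Effect of adjusting.** Assume 4 to 10% users at 5 to 40 mg a day and c of 0.25 to 0.5. Adding dose as a covariate raises power from 0.08–0.28 to about 0.56 (raw) and from 0.29–0.53 to 0.65–0.69 (log), with type I error near 5%. This is a favourable case, because the simulated habitual dose is added in full and in proportion. The documents give no share of users, SD or baseline correlation from which to compute the real gain.

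**7. One month.** 40 × 30 = 1,200 mg at most, which is 24 units on the arm mean at c = 0.5 (1,200 × 0.5 / 25). The plan offers no monthly difference to set against this.

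**The case against.** A reader might infer that one eligible patient can cancel or create the whole planned effect, or that a few of them decide the result. The documents do not support this.

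- The factor 0.25 is the break-even value, not one taken from the plan. On the protocol's own implied scale the shift stays below 0.8.
- Section 10.2.2 provides a log transformation for non-normal data. A patient 20 units above means of about 3 is just the kind of skew that would prompt it, and on that scale the shift is a fraction of the expected effect.
- Allocation is randomised and double blind, so there is no bias on average. A single extreme value also inflates the SD, which protects against false positives.
- The 0.8 difference belongs to 48 hours, while the endpoint covers a month.
- The case needs a patient at the ceiling who continues the full dose, and nothing says how many users will enrol. With one or two, a dose slope would rest on a few high-leverage patients.

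All of this stands and limits the size of the claim. It does not remove the gap. The log scale softens the shift, but under step 5's assumptions power still depends on where one such patient falls. Freedom from bias does not restore lost power.

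**Conclusion.** The gap is confirmed from the text: opioid users up to 40 mg a day may enter, their continued use is counted, and the comparison makes no allowance for it. The consequence is lost power and exposure to chance imbalance, not bias and not extra false positives.

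Its size is conditional. For one patient at the ceiling, the 48-hour raw shift is 0.13 to 0.79 on the protocol's implied scale and reaches 0.8 or more only if c is at least 0.25. On the log scale it is 28 to 41% of the expected effect for c of 0.25 to 0.5. All of this assumes that the habitual dose continues and is counted. The effect on the one-month endpoint cannot be judged, because no difference is stated for it. The plan should be changed, at a priority that suits a secondary endpoint.

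**What to change.** - Leave eligibility as it is.
- Record preoperative daily opioid dose as a number before randomisation. It must be established to apply 3.2.5, but neither section 6.1 nor Appendix A provides a numeric field for it.
- In 10.2.2, replace the t-test with a linear model containing arm and that dose, on the same raw or log scale the plan would have used. If very few patients use opioids, enter any use versus none instead. Fix the threshold for that choice before unblinding.
- Add a sensitivity analysis in patients with no preoperative daily opioid. The subgroup is defined before treatment, so the randomised comparison within it is preserved.
- State the morphine-equivalent conversion used, and reconcile the 45 per group in 10.2.2 with the 25 per arm in 10.3.

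The cost is one data field, one degree of freedom and some SAP wording. If almost no users enrol, the gain will be small.

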3.3 Inclusion of Women and Minorities

Women of all races and ethnicities who meet the above-described eligibility criteria are eligible to participate in this study.

We expect approximately 5% of study participants to be Hispanic/Latino (N=5). We plan to enroll at least 10% Black or African American (N=10), 1% American Indian/Alaska Native (N=1), 5% Asian (N=5). Should we not meet or exceed these estimates, the PI will engage the Cancer Center Health Equity Advisory Group to discuss strategies to enhance recruitment in these target populations.

**THE USE OF LIPOSOMAL BUPIVACAINE FOR PAIN CONTROL FOLLOWING
MASTECTOMY AND IMMEDIATE IMPLANT BASED BREAST RECONSTRUCTION**

Wake Forest Baptist Comprehensive Cancer Center
CCCWU # 99517

4.0 Registration Procedures

All patients entered on any WFBCCC trial, whether treatment, companion, or cancer control trial, **must** be linked to the study in EPIC within 24 hours of Informed Consent. Patients **must** be registered in WISER prior to the initiation of treatment.

You must perform the following steps in order to ensure prompt registration of your patient: All patients will be registered in WISER

1.

To complete the registration process, the study team will:

- assign a patient study number
- notify the pharmacy via faxed physician order form
- register the patient on the study

5.0 Study Outcomes and Study Measures

5.1 Primary Outcome

5.1.1 The primary outcome of this study is the mean visual analog scores (scale of 0-10) within the first 48 hours postoperatively. This will be measured every 12 hours for the first 48 hours and will be assessed by the level of breast pain associated with arm movements while eating.

5.1.1.1 Visual analog scores in mastectomy patients with oral and IV narcotics are approximately 5.0 at 24 hours and 4.8 at 48 hours¹⁷

5.1.1.2 For patients with local infiltration of Liposomal bupivacaine after implant based reconstruction, visual analog scores at 24hrs were 3.8 on average¹⁸

5.2 Secondary Outcomes

5.2.1 Area under the curve visual analog scores (scale 0-10) during the first 48 hours postoperatively.

5.2.1.1 For patients undergoing submuscular augmentation mammoplasty, the area under the curve for pain scores at 72 hours for liposomal bupivacaine infiltration is 441 +/- 182 and for bupivacaine infiltration is 461 +/- 181²⁰

5.2.2 Morphine equivalents used within the first month postoperatively

THE USE OF LIPOSOMAL BUPIVACAINE FOR PAIN CONTROL FOLLOWING MASTECTOMY AND IMMEDIATE IMPLANT BASED BREAST RECONSTRUCTION

Wake Forest Baptist Comprehensive Cancer Center
CCCWU # 99517

- 5.2.2.1 The number of doses of oral narcotics (hydrocodone-acetaminophen 1 tablet) for patients with immediate tissue expander reconstruction without other measure of pain control has been 4.2 at 24 hours and 4.0 at 48 hours¹⁷. This is approximately 3.3 morphine equivalents
- 5.2.2.2 We would expect the patients treated with liposomal bupivacaine to use an average of 2.5 intravenous morphine equivalents at the 48-hour point and decreased morphine equivalents in the liposomal bupivacaine over the first postoperative month.
- 5.2.3 Length of stay for hospitalization after mastectomy and breast reconstruction
 - 5.2.3.1 Length of stay for patients undergoing mastectomy and immediate reconstruction has been shown to be 41-47 hours on average²¹
 - 5.2.3.2 We believe liposomal bupivacaine will shorten this time to 36 hours±12 in the liposomal bupivacaine group, but not in the bupivacaine groups.
- 5.2.4 Readmission rates to the hospital within 2 months after mastectomy and breast reconstruction
 - 5.2.4.1 Patients who underwent tissue expander breast reconstruction have a readmission rate of approximately 4.34%²². We anticipate a readmission rate of approximately 2% Patients will be informed that if they are expected to undergo an axillary lymph node dissection at the time of surgery then they will be excluded from the study. Patients who are undergoing sentinel lymph node biopsies will be included in the study, but if their nodes are positive and there is an intraoperative decision to pursue axillary lymph node dissection they will subsequently be excluded from the study.
- 5.2.5 Frequency of postoperative opioid related adverse effects within the first week of surgery. This includes nausea, vomiting, pruritus, allergy, respiratory depression.
 - 5.2.5.1 After immediate breast reconstruction with implants, patients receiving bupivacaine had a 40% incidence of nausea and vomiting. Those not receiving a local anesthetic had a 75% incidence of nausea and vomiting¹⁷
 - 5.2.5.2 We predict a 30% incidence of opioid related adverse events in our liposomal bupivacaine group
- 5.2.6 Trajectory of postoperative recovery from pain within the first 2 months
 - 5.2.6.1 Growth curve analysis of pain intensity with movement scores over the first two months, using an initial log (time) model and a Bayesian change point analysis
 - 5.2.6.2 Groups will be compared for intercept and slope of the trajectory of pain intensity up to the first change point
 - 5.2.6.3 For the entire population, the impact of the optimism-catastrophizing continuum and other predictive factors for intercept and slope will be explored

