2.2 Secondary Objective(s)

- 2.2.1 To evaluate the effect of liposomal bupivacaine on cumulative pain control within the first 48 hours after mastectomy and breast reconstruction
- 2.2.2 To evaluate the effect of liposomal bupivacaine on the amount of postoperative narcotic use after mastectomy and breast reconstruction for the first month after surgery
- 2.2.3 To evaluate the effect of liposomal bupivacaine on length of hospital stay after mastectomy and breast reconstruction
- 2.2.4 To evaluate the effect of liposomal bupivacaine on hospital readmission rates a within 2 months after mastectomy and breast reconstruction
- 2.2.5 To evaluate the effect of liposomal bupivacaine on the occurrence of opioid adverse effects within the first week of surgery after mastectomy and breast reconstruction
- 2.2.6 To evaluate the effect of liposomal bupivacaine on the trajectory of postoperative pain control within 2 months after mastectomy and breast reconstruction

THE USE OF LIPOSOMAL BUPIVACAINE FOR PAIN CONTROL FOLLOWING
MASTECTOMY AND IMMEDIATE IMPLANT BASED BREAST RECONSTRUCTION

Wake Forest Baptist Comprehensive Cancer Center
CCCWU # 99517

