6.0 Treatment Plan

**THE USE OF LIPOSOMAL BUPIVACAINE FOR PAIN CONTROL FOLLOWING
MASTECTOMY AND IMMEDIATE IMPLANT BASED BREAST RECONSTRUCTION**
Wake Forest Baptist Comprehensive Cancer Center
CCCWU # 99517

	Preoperative Visit	Day of Surgery	Upon discharge home	1 st 12hr post discharge	2 nd 12hr post discharge	3 rd 12hr post discharge	4 th 12hr post discharge	1 week postop	3 weeks postop	5 weeks postop
Life Orientation Test-Revised	X									
PROMIS- Depression	X									
PROMIS- Anxiety	X									
Pain Catastrophizing Scale	X									
Baseline Pain Assessment	X									
Enrollment and informed consent	X									
Receive surgical site infiltration of Exparel or bupivacaine		X								
Q 12 hour pain scores				X	X	X	X			
Patent diary of narcotic use and pain rating			X					X		
Disability assessments								X	X	X
Pain assessments								X	X	X

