The study will be double blinded to both patients and providers including plastic and general surgeons involved in their operative care. We will enroll our patients in pharmacy randomization program, in which the pharmacy will deliver the appropriate medication per assigned group.

To monitor our primary outcomes, patients will be asked to rate their pain level on a visual analog scale (Table 2, Appendix Z) with activity every 12-hours after surgery during their post-procedure stay. The activity for which they will rate their pain will be the arm movements associated with eating. In the hospital, their visual analog scores will be provided to each patient in person by their nurse every 12 hours. Subject's pain scores will continue to be recorded every 12 hours via a phone call from a study team member for the first 48 hours after discharge. Additionally, while in the hospital, the amount of narcotics used will be recorded and converted into morphine equivalents.

Upon discharge, patients will be given a sheet to record their pain level and the amount of narcotics & benzodiazepines used (Appendix K). Both the amount of narcotics & benzodiazepines and the pain level are to be reported at the time of taking any narcotics & benzodiazepines. Patients will follow up with our clinic at 1 week, 3 weeks, and 5 weeks postoperatively. At week 1 patients will bring in their medication and pain diary, and fill out a pain assessment (Appendix G) in addition to a questionnaire assessing breast cancer surgery

THE USE OF LIPOSOMAL BUPIVACAINE FOR PAIN CONTROL FOLLOWING MASTECTOMY AND IMMEDIATE IMPLANT BASED BREAST RECONSTRUCTION

Wake Forest Baptist Comprehensive Cancer Center
CCCWU # 99517

disability (Appendix H)²³. During subsequent appointments made at 3 and 5 weeks postoperatively, they will be assessed and receive the pain assessment and breast cancer surgery disability assessments as well. When tissue expansion is initiated will be determined by the primary surgeon, but we will track the dates of the initiation of expansion as this will impact pain scores within the electronic medical record.

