9.0 Data Management

Informed consent document	EPIC
Protocol registration form	WISER/OnCore
Life Orientation Test-Revised	REDCap
PROMIS- Depression	REDCap
PROMIS- Anxiety	REDCap
Pain Catastrophizing Scale	REDCap
Visual analog scores	REDCap
Daily Pain Diary and Pain Rating	REDCap
Weekly Disability Assessment	REDCap
Adverse Effects	WISER

THE USE OF LIPOSOMAL BUPIVACAINE FOR PAIN CONTROL FOLLOWING
MASTECTOMY AND IMMEDIATE IMPLANT BASED BREAST RECONSTRUCTION

Wake Forest Baptist Comprehensive Cancer Center
CCCWU # 99517

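### Opioid use is a first-month outcome, but the diary is due back at week 1, so as scheduled a cumulative one-month total cannot be built

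*Combined protocol and SAP*

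**What the plan says.** **Outcome.** Objective 2.2.2 concerns "the amount of postoperative narcotic use after mastectomy and breast reconstruction for the first month after surgery". Section 5.2.2 names the outcome as "Morphine equivalents used within the first month postoperatively". Section 5.2.2.2 gives an expected value at 48 hours and, in the same sentence, expects "decreased morphine equivalents in the liposomal bupivacaine over the first postoperative month".

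**Collection to week 1.** Under section 6.1, inpatient narcotics are recorded and converted to morphine equivalents. At discharge the patient receives the Appendix K sheet, which has columns for drug with dose, number of pills, time and pain rating. Amounts and pain level "are to be reported at the time of taking any narcotics & benzodiazepines"; no stop date is given. Then: "At week 1 patients will bring in their medication and pain diary". In the section 6.0 schedule, the row "Patent diary of narcotic use and pain rating" is marked at discharge and at 1 week only.

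**Collection after week 1.** Section 6.1 continues: "During subsequent appointments made at 3 and 5 weeks postoperatively, they will be assessed and receive the pain assessment", together with the disability form. Item 6 of the pain assessment (Appendix G) asks whether prescription pain pills were taken in the past 24 hours, has the patient circle a drug from a list of three opioid products and Valium, and asks for one pill count.

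**Analysis.** Section 10.2.2 plans a t-test, after log transformation if the data are not normal. It cites a 48-hour figure from prior studies and does not restate the window.

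**The concern.** The outcome is a quantity accumulated over a month, while the instrument that measures it is handed in after a week. If the plan is followed exactly, the analyst has no morphine-equivalent amount for about days 8 to 30, and the expectation in 5.2.2.2 cannot be tested as written. No rule for prescription or refill data, imputation or extrapolation fills the gap.

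Two things are at stake. The trial could not show whether an early opioid saving persists or is offset later. And if a week-1 total were used in place of the month, the estimated relative reduction could differ from the true one-month reduction. Later use may not be negligible: section 6.1 says that the start of tissue expansion will affect pain scores and leaves its timing to the surgeon, although the documents give no dates. Diary entries that are not made and collected at the time are hard to recover afterwards.

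**Working it through.** **The plan's own figure.** Section 10.2.2 states 45 per group for an effect size of 0.6, two-sided alpha 0.05 and 80% power. This reproduces: 44 per group by the normal approximation, 44.6 (so 45) by the t-test. The figure is in standard-deviation units and says nothing about the window. That 10.3 plans 25 per arm is a separate matter.

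**Coverage.** The visits are taken as days 7, 21 and 35, and the month as 30 days. The documents do not define the month.
- Continuous capture (inpatient record plus diary): days 1 to 7, so 7/30 = 23%.
- Remaining: 30 − 7 = 23 days, or 23/30 = 77%. This is a share of days, not of opioid use.
- The week-3 recall covers about 1 of those 23 days; week 5 (day 35) falls outside the month.
- For a month of 28 to 31 days, coverage is 7/28 = 25% to 7/31 = 23%.

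**Can the recalls fill the gap?** No. Each covers 24 hours, asks for no tablet strength, and gives one count that may combine opioids with Valium. They allow a crude comparison of recent use between arms, but they cannot be reliably converted to morphine equivalents or summed to a total.

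**Share of use in the gap.** The documents do not say how use declines. Assume exponential decline with half-life h days, so that the share of all use taken by day t is F(t) = 1 − 2^(−t/h). The share of the 30-day total falling in days 8 to 30 is [F(30) − F(7)] / F(30).

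| h (days) | F(7) | F(30) | Share in days 8–30 | F(30)/F(7) |
|---|---|---|---|---|
| 2 | 0.912 | 1.000 | 8.8% | 1.10 |
| 4 | 0.703 | 0.994 | 29.3% | 1.42 |
| 7 | 0.500 | 0.949 | 47.3% | 1.90 |

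**Bias if a week-1 total replaced the month.** Let w = F(7)/F(30) be the share of the control arm's 30-day use that falls in week 1. Let r1 and r2 be the relative reductions in days 1–7 and days 8–30. The month reduction is R = w·r1 + (1 − w)·r2, and the week-1 analysis estimates r1.
- Effect confined to week 1 (r2 = 0): r1/R = 1/w = F(30)/F(7), that is 1.10, 1.42 or 1.90.
- Constant proportional effect (r2 = r1): r1/R = 1, no bias.
- Benefit larger later (r2 > r1): r1/R < 1, so the week-1 figure understates the month.

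**Sheets needed to extend the diary.** Appendix K has about 50 rows. At an assumed 2 to 4 entries a day, one sheet lasts 50/2 = 25 to 50/4 = 12.5 days. The gap between visits is 14 days, and 14 × 4 = 56 rows, so at 4 entries a day two sheets are needed per gap.

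**The case against.** **The diary might run longer.** Appendix K has no printed stop date, section 9.0 lists "Daily Pain Diary and Pain Rating" without an end date, and the table of contents calls Appendix G a daily diary although the form itself is headed as a pain assessment. A reader could infer daily collection through the month. Equally, a reader could infer that no opioid data exist after week 1, or that a month total is impossible in principle. The documents support none of these. Text and schedule agree on return of the diary at week 1 and on Appendix G at weeks 1, 3 and 5; the recalls do exist; and a patient could keep writing. What stands is narrower: no return of the diary after week 1 is planned.

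**Competing horizons.** A reader might infer that the protocol sets three conflicting horizons for opioid use: 48 hours, one week and one month. It does not. Week 1 is when the diary comes back, and the first-week window in 5.2.5 belongs to opioid adverse effects. Section 5.2.2.2 gives 48 hours and the month together without conflict. Section 10.2.2 can inherit the month from 2.2.2 and 5.2.2, so stating its window is a clarification.

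**Week 1 may be enough.** Section 1.0 puts the local effect at up to 72–96 hours, so a difference is most likely to arise inside the recorded week. That is reasonable, but it argues for restating the objective, not for leaving a month that is not measured.

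**Electronic records.** Section 6.1 says that some secondary outcomes are tracked by electronic record. The list is not closed, but it names length of stay, opioid adverse effects and readmission, and not opioid use at home.

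**Conclusion.** The point holds as a mismatch between an outcome window and its data collection. As scheduled, about 7 of 30 days are captured continuously and about 23 have no usable quantity, so a stated secondary objective cannot be answered as written.

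The size of the consequence is uncertain. The factors of 1.1 to 1.9 rest on an assumed exponential decline with half-lives of 2 to 7 days and on an effect confined to week 1. A reader might infer that a week-1 total must overstate the month. It overstates only if the relative effect shrinks after day 7, and no passage says that a week-1 total will be reported as the month. If opioid use stops early, little is lost.

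The outcome is secondary and the 48-hour primary outcome is untouched. It should be corrected, because the remedy is cheap and the missing data are hard to recover later.

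**What to change.** **Preferred: measure the month.** Continue the Appendix K diary to day 30. Hand out enough sheets to cover each 14-day gap between visits (two per gap at 4 entries a day), collect them at the existing week-3 and week-5 visits, and mark this in the section 6.0 schedule. Compute cumulative opioid morphine equivalents to day 30, with benzodiazepines excluded from that total. Cost: 30 − 7 = 23 more days of diary keeping per patient, extra sheets, data entry at two visits that already take place, and possibly more missing entries.

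**Alternative: restate the window.** Reword 2.2.2, 5.2.2 and 5.2.2.2 as use to the week-1 visit, and report the week-3 and week-5 items only as recent use. Cost: text changes only, but the objective shrinks from a month to a week, and persistence of any saving cannot be assessed.

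**Either way,** state the analysis window in 10.2.2.
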